5.5 Analyses of secondary objectives

The analysis of the secondary objectives will be also performed on the analysis population.

5.5.1 Description of comorbidities related to GCs

Current and past comorbidities of GCA patients (comorbidities related to GCs intake) will be coded using the medical dictionary MedDRA®. They will be described by MedDRA SOC and PT overall and by type of physicians who follows the patient.

Among the patients with comorbidities related to GCs intake the number and percentage of patients with at least one ongoing specific treatments(s) will be calculated.

A listing of treatments taken by patients with comorbidities related to GCs will be presented.

5.5.2 Description of GCA characteristics

First the following parameters will be presented:

- Time between diagnosis and inclusion will be described as quantitative variable (months) ([APPENDIX](#))
- Type of patient
 - Proportion of incident patients (newly diagnosed): patients with a diagnosis of GCA \leq 6 weeks from inclusion
 - Proportion of prevalent patients (not newly diagnosed): patients with a diagnosis of GCA $>$ 6 weeks from inclusion.

Then the following endpoints will be described overall and by type of patient (prevalent/incident), by type of diagnosis (time between the first medical events related to GCA and diagnosis to GCA as qualitative variable in 3 classes early/in standard time/late diagnosis), and by type of physicians who follows the patient.

- Initial presentation:
 - Proportion of patients with at least one cranial manifestation at diagnosis and the proportion of each symptom of this family (Headaches/ Scalp sensitivity / Anomalies of the temporal arteries (temporal artery sensitivity or decreased pulsation) / Ischemia-related vision impairment and-or loss / Mouth pain or jaw claudication during mastication / Stroke or transient ischemic attack (TIA) / Other)

Listing of Ischemia-related vision impairment / loss and other cranial manifestation at diagnosis will be presented.

- Proportion of patients with at least one PMR symptom at diagnosis and the proportion of each symptom of this family (Morning stiffness and-or pain in the shoulder girdle/ Morning stiffness and-or pains in the pelvic girdle/ Inflammatory arthromyalgia/ Peripheral arthritis/ Other)

A listing of other PMR symptom will be presented.

- Proportion of patients with at least one extracranial event (excluding PMR) at diagnosis and the proportion of each symptom of this family (Thoracic or abdominal aortic aneurysm and-or dilatation/ Aortitis and-or involvement of aortic branch(s) in imaging/ Angina and-or Myocardial infraction/ Claudication of an upper limb and-or claudication of a lower limb/ Sign of subclavian stenosis (asymmetry of pulse, blood pressure, subclavian murmur)/ Other)

A listing of other extracranial events (excluding PMR) will be presented.

- Value of ESR (mm/1st h) and CRP (mg/L) at diagnosis and at inclusion.
- Proportion of patients having abnormal value of ESR (ESR $>$ 50 mm/h)/CRP (CRP $>$ 25 mg/L) at diagnosis
- Proportion of patients having abnormal value of ESR (ESR $>$ 50 mm/h)/CRP CRP $>$ 25 mg/L) at inclusion
- Proportion of patients with at least one general sign at diagnosis and the proportion of each sign (fever $>$ 38°C with no other etiology than GCA, weight loss and its value (%), alteration of the general condition)

For the value of ESR and CRP at diagnosis, only value measured in the previous month, the current month and the month following the date of diagnosis will be considered. For values at inclusion, only measures done within 6 month before the date of inclusion will be considered.

A listing of other initial characteristics related to GCA at diagnosis will be presented.

- Clinical form:
 - Proportion of patients with at least one relapse
 - In patient with at least one relapse:
 - Number of relapses per patient
 - Time between first relapse and diagnosis (months) ([APPENDIX](#))
 - Mean time between 2 consecutive relapses (months) ([APPENDIX](#))
 - The following information will be summarized by relapse:
 - Proportion of used criteria to assess relapse (Clinical/ Biological/ Imagery/ Other)
 - Proportion of patients using GCs just before the relapse
 - GCs dose at relapse diagnosis (mg/day)
 - Proportion of relapses of patients with Immunosuppressants just before the relapse
 - Proportion of relapses of patients with Targeted biologic therapy just before the relapse
 - Proportion of relapses of patients using other treatments just before the relapse
 - Proportion of relapses for which Glucocorticoids (GCs) were used as medical care for the relapse
 - GCs dose used for relapse medical care (mg/day)
 - Proportion of relapses for which Immunosuppressants were used as medical care for the relapse
 - Proportion of relapses for which Targeted biologic were used as medical care for relapse
 - Proportion of relapses for which other GCA (HORTON) treatments were used as medical care for relapse.
 - Distribution of GCs dependence
 - Current dose at inclusion (mg/day)
 - Number of kinetics per patient since diagnosis
 - Time between first kinetic and diagnosis (months) ([APPENDIX](#))
 - Proportion of patients with at least one kinetic ongoing at inclusion
 - Mean time between 2 consecutive kinetics (months) ([APPENDIX](#))
 - Total cumulative GCs dose according to investigator (excluding IV bolus) since diagnosis (mg) ([APPENDIX](#))
 - The following information will be summarized by Kinetic:
 - Kinetic duration (months) ([APPENDIX](#))
 - Proportion of kinetics with IV initial administration (bolus) (Yes/No)
 - If yes, total number of days
 - IV bolus dose (mg)
 - Switch PO dose (mg/day)
 - Cumulative dose according to investigator (mg)
 - Proportion of kinetics for which a corticotherapy for GCA (Horton) care has restarted after the kinetic
 - Proportion of patients with at least one GCA complication
 - Proportion of patients with ongoing specific treatment(s) for GCA complications

Current and/or past GCA complications according to the investigator judgment will be coded using the medical dictionary MedDRA®. They will be described by SOC and PT overall and by type of physicians who follows the patient.

To determine the potential factors associated to relapse, a logistic regression will be used. The outcome variable will be relapse (Yes/ No). First, a univariate analysis will be conducted. All significant

factor at the 20% threshold will be selected for a multivariate analysis. A backward elimination procedure will be used with a threshold of 5%.

The associated factors that will be studied are:

- Age (in classes)
- Gender (Male/Female)
- BMI at diagnosis (in classes)
- Smoking status (Smoker/ Former smoker/ Non-smoker ever / Unknown)
- Type of patient (Prevalent or incident)
- Physician who referred the patient (General practitioner/ Ophthalmologist / Neurologist/ Emergency/ Internist/ Rheumatologist/Other),
- Patient considered with late diagnosis by the physician who referred him (Yes/ No)
- Patient considered with late diagnosis according to calculated time interval between the first medical events related to GCA and diagnosis : (Yes/No)
- Patient with at least one cranial GCA symptom at diagnosis (Yes/No),
- Patients with at least one PMR symptom at diagnosis (Yes/No),
- Patient with at least one extracranial GCA symptom at diagnosis (Yes/No),
- Patient with abnormal value of ESR at diagnosis (ESR>50 mm/h)
- Patient with abnormal value of CRP at diagnosis (CRP> 25 mg/L) (Yes/No),
- Patient with fever (>38°C) at diagnosis (Yes/No),
- Patient with weight loss at diagnosis (Yes/No),
- Patient with alteration of the general condition at diagnosis (Yes/No),
- Patient has taken at least one immunosuppressant since diagnosis (Yes/No)
- Patient has taken at least one targeted biological therapy since diagnosis (Yes/No)
- Patient has taken at least one other long-term treatment for the medical care of GCA since diagnosis (Yes/No)
- VAS score (global arteritis activity) by patient (>50mm/≤50mm)
- VAS score (global arteritis activity) by physician (>50mm/≤50mm)
- Cumulative dose of GCs (mg)

- GCA activity

- Scores of the physician global arteritis activity VAS will be analysed as quantitative variables and in classes (≤ 50 ; > 50 mm).
- Scores of the patient global arteritis activity VAS will be analysed as quantitative variables and in classes (≤ 50 ; > 50 mm).

The VAS scores of physician and patient will be divided into classes. The same cut-off (≤ 50 ; > 50 mm) for the two scores will be defined by CHUGAI according to their medical relevance.

In this case, the concordance between the scores of the patient and physician global arteritis activity VAS will be evaluated using the kappa K coefficient, which will be interpreted as follows:

- $K < 0.0$: No match
- $0.0 \leq K \leq 0.2$: Poor agreement
- $0.2 < K \leq 0.4$: Fair agreement
- $0.4 < K \leq 0.6$: Moderate agreement
- $0.6 < K \leq 0.8$: Good agreement
- $K > 0.8$: Very good agreement

To evaluate the GCA activity, the score of the physician global arteritis activity VAS will be used. For this score a threshold value = 10 mm was defined and validated by CHUGAI.

Patients with physician's VAS score less than or equal to 10 mm will be considered with "non-active GCA", while patients with physician's VAS score greater than 10 mm will be considered with "active GCA".

In this case, the potential associated factors with the increase of the GCA activity will be studied by logistic regression.

The outcome variable will be GCA (active/ Non-active). First, a univariate analysis will be conducted. All significant factor at the 20% threshold will be selected for a multivariate analysis. A backward elimination procedure will be used with a threshold of 5%.

The associated factors that will be studied are:

- Age (in classes)
- Gender (Male/Female)
- BMI at diagnosis (in classes)
- Smoking status (Smoker/ Former smoker/ never smoker/unknown)
- Prevalent or incident patient,
- Physician who referred the patient,
- Patient considered with late diagnosis by the physician who referred him (Yes/ No)
- Patient with at least one cranial GCA symptom at diagnosis (Yes/No),
- Patients with at least one PMR symptom at diagnosis (Yes/No),
- Patient with at least one extracranial GCA symptom at diagnosis (Yes/No),
- Patient with abnormal value of ESR (ESR>50 mm/h) at diagnosis
- Patient with abnormal value of CRP (CRP> 25 mg/L) at diagnosis (Yes/No),
- Patient with fever at diagnosis (Yes/No),
- Patient with weight loss at diagnosis (Yes/No),
- Patient with alteration of the general condition at diagnosis (Yes/No),
- Number of relapses
- Patient has taken at least one immunosuppressants since diagnosis (Yes/No)
- Patient has taken at least one targeted biological therapy since diagnosis (Yes/No)
- Patient has taken at least one other long-term treatment for the medical care of GCA since diagnosis (Yes/No)
- Patient considered with late diagnosis according to calculated time interval between the first medical events related to GCA and diagnosis (Yes/No)
- Cumulative dose of GCs

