The index date was defined as the date of first occurrence of GCA code and cases were considered being incident if the GCA code first occurred after a minimal follow-up of 2 years. A treatment sequence was defined as the start of a new drug or the resumption of the same drug after a stop of drug dispensing ≥ 3 months. Annual incidence rates were calculated for the period 2009 to 2015 by using the people recorded in the EGB database as denominator.

Briefly, the results were the following: among the 752,717 patients recorded in the EGB database, 241 people fulfilled inclusion criteria with a mean follow-up of 3.7 (± 2.6) years. Annual incidence was ranging between 7 and 10/100,000 people ≥ 50 years-old that is 2300 patients/year. Demographic analyses showed that 72% of the patients were females and that mean age was 77.5 (± 8.9) years. 74.3% of the patients had at least one proxy (i.e ICD-10 code or a treatment) for hypertension, 39.4% for depression/insomnia and 33.6% for osteoporosis. After index date, temporal artery biopsy (TAB) was performed in 43.2%, high-resolution color Doppler ultrasound in 35.3% and 18FDG-positron emission tomography (PET) in 11.6%.

Regarding treatments, 84.3% of the patients used only GCs while 16.7% also received 1 to 3 adjunctive medications, mainly MTX. Mean 1st GCs sequence duration was 17.2 months (± 16.5) in 96.6% of the patients.

EGB database strengths included comprehensive patient demography, epidemiology, diagnostic methods and treatment sequences. In contrast, limited data were available for comorbidities (as only proxies were described), clinical presentations (cranial, polymyalgia rheumatica [PMR], extracranial), clinical forms (relapsing, GCs-dependant), doses of GCs used, cumulative GCs doses and GCs associated toxicities. In addition, patient journey was poorly described given that patients may be first seen by a variety of physicians according to their first signs and symptoms (e.g. ophthalmologist for blurred vision, neurologist for headache, etc.), data which was not available in the EGB database analysis.

The proportions of use of TAB, Ultrasound or PET have also to be confirmed as they thought to be unusually performed in the EGB analysis.

We propose to conduct an observational study aiming to describe GCA management and patient characteristics in France.

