5.3.1 Case report form

No information related to patient identity (initials, full date of birth, etc) will be entered in the eCRF.

The following information will be recorded in the eCRF using the data available in the medical file or collected during the visit (as part of the routine patient management):

- » Date of the inclusion visit (the only study visit) and type of visit (outpatient visit, day hospital, in-patient hospitalisation).
- » Patient eligibility criteria.
- » Demographic data:
 - Year of birth, gender,
 - Smoking status (smoker, never smoker),
- » Clinical data:
 - Height, weight (at diagnosis, at the inclusion visit)
 - Medical history:
 - significant past and current comorbidities (e.g. diabetes, high blood pressure, dyslipidaemia, osteoporosis, neuropsychiatric disorders,

depression, insomnia, serious infection disease, parasitic diseases, cancer, stroke, coronary artery disease, ischemic cardiopathy, peripheral artery diseases, adrenal insufficiency, cataract, glaucoma, gastro-intestinal ulcer, digestive perforation, other significant history),

- start and stop date (month, year) of comorbidities
- Comorbidities related to GCs for GCA patients (i.e. which appeared or worsened during GCs treatment according to the investigator judgement).

» GCA patient journey:

- Incident or prevalent patient:
 - Newly diagnosed (i.e. incident) patient will be defined as patient with GCA diagnosis within the last 6 weeks before visit
 - Not newly diagnosed (i.e. prevalent) patients will be defined as patient with GCA diagnosis more than 6 weeks before visit
- Date of initial diagnosis
- Date of GCA signs/symptoms (month and year)
- Physician(s) who referred the patient (General Practitioner, Ophthalmologists, Neurologist, Emergency, Internist, Rheumatologist, Other).

» GCA characteristics:

- Initial presentation at diagnosis and inclusion visit:
 - Cranial (localized headache, scalp tenderness, temporal artery tenderness or decreased pulsation, ischemia-related vision impairment / loss, mouth or jaw pain upon mastication, stroke or transient ischaemic attack (TIA), other)
 - PMR (morning stiffness and/or pain in the shoulder and/or pelvic girdles, inflammatory arthromyalgia, peripheral arthritis, other)
 - Extracranial (large-vessel GCA i.e. thoracic or abdominal aortic aneurysm, myocardial infarction, dilatation, limb claudication, subclavian stenosis, other)
 - ESR/CRP
 - General signs: fever, weight loss (%), health status modification

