9.3.2 Description of GCA characteristics

Table 14 - Efficacy analysis – Description of GCA characteristics - Analysis population (N=XX)

Parameter	Statistics	Total (N=XX)
Time between diagnosis and inclusion (months)	Mean SD Median [Q1 ; Q3] [Min ; Max] Filled, n(%) Missing, n(%)	
Type of patient * Incident Prevalent	n(%) n(%) Filled, n(%) Missing, n(%)	

*Incident if diagnosis of GCA ≤6 weeks from inclusion
Prevalent if diagnosis of GCA >6 weeks from inclusion
The percentages are calculated compared to filled data
STUDY : CHUGAI-ARTEMIS - Edition date: DDMMYY
Pgm : EFFICACY\GCA.SAS

Table 15 - Efficacy analysis – Initial presentation of GCA - Analysis population (N=XX)

Parameter	Statistics	Total (N=XX)
Patient with at least one cranial manifestation at diagnosis No Yes	n(%) n(%) Filled, n(%) Missing, n(%)	
Cranial manifestation* Headaches Scalp sensitivity Anomalies of the temporal arteries Ischemia-related vision impairment and-or loss Mouth pain or jaw claudication during mastication Ischemia-related vision impairment and-or loss Stroke or transient ischemic attack (TIA) Other	n(%) n(%) n(%) n(%) n(%) n(%) n(%) n(%)	
Patient with at least one PMR symptom at diagnosis No Yes	n(%) n(%) Filled, n(%) Missing, n(%)	
PMR symptom * Morning stiffness and-or pain in the shoulder girdle Morning stiffness and-or pains in the pelvic girdle Inflammatory arthromyalgia Peripheral arthritis/ Other	n(%) n(%) n(%) n(%) n(%)	
Patient with at least one extracranial event (excluding PMR) at diagnosis No Yes	n(%) n(%) Filled, n(%) Missing, n(%)	
Extracranial event (excluding PMR)* Thoracic or abdominal aortic aneurysm and-or dilatation Aortitis and-or involvement of aortic branch(s) in imaging Angina and-or Myocardial infraction Claudication of an upper limb and-or claudication of a lower limb Sign of subclavian stenosis	n(%) n(%) n(%) n(%) n(%)	

Table 15 - Efficacy analysis – Initial presentation of GCA - Analysis population (N=XX)

Parameter	Statistics	Total (N=XX)
Other	n(%)	
Value of ESR (mm/1st h) at diagnosis	Mean SD Median [Q1 ; Q3] [Min ; Max] Filled, n(%) Missing, n(%)	
Value of ESR (mm/1st h) at diagnosis in classes ≤50 mm/h >50mm/h	n(%) n(%) Filled, n(%) Missing, n(%)	
Value of ESR (mm/1st h) at inclusion	Mean SD Median [Q1 ; Q3] [Min ; Max] Filled, n(%) Missing, n(%)	
Value of ESR (mm/1st h) at inclusion in classes ≤50 mm/h >50mm/h	n(%) n(%) Filled, n(%) Missing, n(%)	

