Value of CRP (mg/L) at diagnosis	Mean SD Median [Q1 ; Q3] [Min ; Max] Filled, n(%) Missing, n(%)	
Value of CRP (mg/L) at diagnosis in classes ≤25 mg/L >25 mg/L	n(%) n(%) Filled, n(%) Missing, n(%)	
Value of CRP (mg/L) at inclusion	Mean SD Median [Q1 ; Q3] [Min ; Max] Filled, n(%) Missing, n(%)	
Value of CRP (mg/L) at inclusion in classes ≤25 mg/L >25 mg/L	n(%) n(%) Filled, n(%) Missing, n(%)	
Patient with at least one general signe at diagnosis No Yes	n(%) n(%) Filled, n(%) Missing, n(%)	
Clinical signs and symptoms* Fever>38°C Weight loss Alteration of the general condition	n(%) n(%) n(%)	
If weight loss: value of weight loss (%)	Mean SD Median [Q1 ; Q3] [Min ; Max] Filled, n(%)	

Table 15 - Efficacy analysis – Initial presentation of GCA - Analysis population (N=XX)

Parameter	Statistics	Total (N=XX)
	Missing, n(%)	

* multiple response possible
 PMR : PolyMyalgia Rheumatica
 ESR : Erythrocyte Sedimentation Rate
 CRP : C Reactive Protein
 The percentages are calculated compared to filled data
 STUDY : CHUGAI-ARTEMIS - Edition date: DDMMYY
 Pgm : EFFICACYGCA.SAS

This table will be presented by type of patient (prevalent/incident), by type of diagnosis and the physician who follows the patient.

Listing 4 : Specification of Ischemia-related vision impairment / loss at diagnosis (N= XX)

Patient ID	Type of patient	Type of diagnosis	Physician who follows the patient	Specification of Ischemia-related vision impairment/loss

STUDY : CHUGAI-ARTEMIS - Edition date: DDMMYY
 Pgm : EFFICACYGCA.SAS

Listing 5 : Specification of other cranial manifestation at diagnosis (N= XX)

Patient ID	Type of patient	Type of diagnosis	Physician who follows the patient	Specification of other cranial manifestation

STUDY : CHUGAI-ARTEMIS - Edition date: DDMMYY
 Pgm : EFFICACYGCA.SAS

Listing 6 : Specification of other PMR symptom at diagnosis (N= XX)

Patient ID	Type of patient	Type of diagnosis	Physician who follows the patient	Specification of other PMR symptom

STUDY : CHUGAI-ARTEMIS - Edition date: DDMMYY
 Pgm : EFFICACYGCA.SAS

Listing 7 : Specification of other extracranial events (excluding PMR) at diagnosis (N= XX)

Patient ID	Type of patient	Type of diagnosis	Physician who follows the patient	Specification of other extracranial events

STUDY : CHUGAI-ARTEMIS - Edition date: DDMMYY
Pgm : EFFICACYGCA.SAS

Listing 8 : Specification of other initial characteristics related to GCA at diagnosis (N= XX)

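### Imaging-dependent extracranial findings are reported without an imaged denominator, so their proportions and subgroup breakdowns are confounded with imaging use, and the composite and both regressions inherit part of this

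*SAP*

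**What the plan says.** The extracranial share is part of the initial-presentation endpoint (Protocol 6.2). SAP 5.5.2 plans the "Proportion of patients with at least one extracranial event (excluding PMR) at diagnosis" and the proportion of each item. Two items concern large-vessel findings: "Thoracic or abdominal aortic aneurysm and-or dilatation" and "Aortitis and-or involvement of aortic branch(s) in imaging". The others are angina or myocardial infarction, limb claudication, signs of subclavian stenosis (pulse or blood-pressure asymmetry, murmur) and a free category.

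The aortitis item is new in the SAP. Protocol 5.3.1 lists "Extracranial (large-vessel GCA i.e. thoracic or abdominal aortic aneurysm, myocardial infarction, dilatation, limb claudication, subclavian stenosis, other", and SAP 5.6 does not mention the addition.

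Table 15 shows "Patient with at least one extracranial event (excluding PMR) at diagnosis" with filled and missing counts. The individual event rows beneath it are multiple-response lines with neither. The footnote reads "The percentages are calculated compared to filled data". The table is repeated by incident/prevalent status, type of diagnosis (early, standard, late) and following physician.

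SAP 3.2 says that no study-specific examination is required. SAP 5.4 and Table 5 record PET, CT angiography and MR angiography each as done or not done, and count only those performed from the month before to the month after diagnosis. The relapse model lists the factor "Patient with at least one extracranial GCA symptom at diagnosis (Yes/No"), and the activity model lists the same one.

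**The concern.** A finding that requires a test can be reported only in people who had the test. If imaging practice differs between internists and rheumatologists, between early and late diagnoses, or between incident and prevalent patients, the imaging-detected rows will differ between those groups even when the disease does not. The primary objective itself describes diagnostic methods by physician type and by delay, so the plan treats such variation as possible.

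The SAP handles neighbouring items differently. Whether an imaging test contributed to the diagnosis is reported only where the test was done. ESR and CRP rows carry filled and missing counts, so an unmeasured patient leaves the denominator. For imaging findings there is no tested denominator, and an unticked row does not separate imaged-negative from never-imaged.

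At stake are a secondary endpoint, its three breakdowns, and one candidate factor in each logistic model.

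**Working it through.** The plan gives no figure to reproduce: there is no sample-size calculation (Protocol 7.1.1) and no expected extracranial share. The size is therefore an illustration.

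**Inputs**
- From the documents: 300 patients planned.
- Assumed, because the documents give none: t = 30% positive if imaged; u = 30% imaged in one subgroup and 60% in the other; c = 5%, 10% or 20% with a clinical extracranial event; 150 patients per subgroup; imaging and clinical events unrelated to imaging-detectable involvement; never-imaged patients treated as negative.

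**Imaging item over all patients** = u × t, which cannot exceed u.
- 0.30 × 0.30 = 9%
- 0.60 × 0.30 = 18%

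True involvement is 30% in both groups.

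**Composite** = 1 − (1 − c)(1 − u × t)

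| c | 30% imaged | 60% imaged | Difference (points) |
|---|---|---|---|
| 5% | 1 − 0.95 × 0.91 = 13.6% | 1 − 0.95 × 0.82 = 22.1% | 8.6 |
| 10% | 1 − 0.90 × 0.91 = 18.1% | 1 − 0.90 × 0.82 = 26.2% | 8.1 |
| 20% | 1 − 0.80 × 0.91 = 27.2% | 1 − 0.80 × 0.82 = 34.4% | 7.2 |

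As a gauge only, since no between-group comparison is planned: in simulation with 150 per group, a Wald 95% interval for the difference excludes zero in about 64% of studies for the imaging item alone. For the composite this falls to about 50%, 40% and 28% at c = 5%, 10% and 20%.

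**Share of composite positives resting on imaging alone** = (composite − c) / composite. Over a wider grid (t = 20% or 40%, c = 5% to 20%, u = 11.6% to 50%) it runs from about 8% (t = 20%, c = 20%, u = 11.6%) to 79% (t = 40%, c = 5%, u = 50%).

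**Regression factor, imaging item alone.** Assume a 30% relapse risk without involvement and a true odds ratio of 2. The odds with involvement are 2 × 0.30/0.70 = 0.857, a risk of 46.2%. Among patients coded No, the share truly involved is t(1 − u)/(1 − t × u).
- u = 30%: 0.21/0.91 = 23.1%; risk 0.30 + 0.231 × 0.162 = 33.7%; odds 0.509; observed odds ratio 0.857/0.509 = 1.68.
- u = 60%: 0.12/0.82 = 14.6%; risk 32.4%; odds 0.478; observed odds ratio 1.79.

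Clinical events in the composite would change these values.

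**Precision of an imaged-only figure.** With 45 imaged of 150, the 95% half-width at 30% is 1.96 × √(0.3 × 0.7/45) = 13.4 points; with 90 imaged it is 9.5 points.

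**The case against.** Five points on the other side carry weight.

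1. A reader might infer that only imaged patients can be positive for extracranial GCA, so that the endpoint largely measures imaging use. The documents do not support this. The composite includes limb claudication, subclavian signs, angina or infarction and a free category, none of which needs large-vessel imaging, and the 8% to 79% range shows that the imaging part may be small or dominant.
2. A reader might also infer that never-imaged patients are counted as negative. No section says so. The composite has a missing row and SAP 5.2.1 leaves missing data unreplaced. What stands is that the coding is undefined.
3. Protocol section 1 reports "18FDG-positron emission tomography (PET) in 11.6" per cent of patients in the earlier claims study. This is tempting as a coverage figure, but it covers PET only, omits CT and MR angiography, and the protocol itself says that these proportions need confirmation.
4. The study describes presentation as documented in usual care, for which an all-patient figure is legitimate. That holds if the figure is labelled as such; it does not make subgroup differences interpretable as differences in disease. Imaging targeted at suspected cases would also reduce the bias.
5. Table 5 already shows imaging use by delay and physician type. This helps for two of the three breakdowns. But it lists each test separately, so the number with any large-vessel imaging cannot be read from it, and it is not split by incident/prevalent status.

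The missing entry in SAP 5.6 is minor, since the protocol list already ends with an open category.

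**Conclusion.** The concern holds in a limited form. The proportion with imaging-defined aortitis cannot exceed imaging coverage; the same is mostly true of aneurysm or dilatation, on the assumption that few are found without imaging. The breakdowns of these rows are confounded with imaging use, and Table 5 does not remove that.

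The composite inherits the problem only in part. In the illustration, a doubling of the imaging item (9% to 18%) becomes a composite gap of 8.6 points with 5% clinical events and 7.2 points with 20%. All these inputs are assumed, imaging is taken as unrelated to involvement, and no test between groups is planned, so the simulated percentages describe how misleading a contrast could look, not an error rate of the plan. The regression factor is also affected, assuming that the extracranial symptom in the model lists is the Table 15 composite; the SAP defines no other variable.

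This is a cheap improvement to a secondary descriptive endpoint. It does not invalidate the study.

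**What to change.** In SAP 5.5.2 and Table 15:

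1. Present clinical extracranial events (limb claudication, subclavian signs, angina or infarction) separately from imaging-detected ones (aortitis or branch involvement, aneurysm or dilatation).
2. Show the number and percentage of patients with at least one of PET, CT angiography or MR angiography, plus relevant imaging recorded as another diagnostic method, overall and in every subgroup column, including incident/prevalent. Give the imaging-detected rows both among imaged patients and over all patients, the latter labelled as detected in usual care and a minimum.
3. Code never-imaged patients as not assessed. Apply the Table 5 window (month before to month after diagnosis) to the imaging findings; SAP 5.5.2 gives extracranial events no explicit window, so without this some positives could fall outside the imaged denominator.
4. In both logistic models use clinical extracranial events, or a three-level factor: imaged positive, imaged negative, not imaged.

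Listing the added item in SAP 5.6 would complete the record.

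Cost: SAP wording, some extra rows in Table 15, a link to the Table 5 data already collected, and a review of the free-text imaging entries. The imaged-only figure comes from a selected subgroup and has a wider interval, so both figures must be shown and labelled.
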